#### 4.3. Primary endpoint

The primary endpoint is the incidence of severe\* symptomatic acute upper and lower respiratory infections†, all grades of severity combined.

\* Severe = leading to oxygen therapy, hospitalization or death

(†) Acute infections considered include sinusitis, otitis media, nasopharyngitis, angina, tracheitis, bronchitis, pulmonary abscess, pneumonia and COPD exacerbations. Documented symptomatic infection with SARS-CoV-2, influenza virus, or respiratory syncytial virus, will be considered by default as a respiratory infection, even in the case of dominant extra-respiratory symptoms.

#### 4.4. Secondary endpoints

The secondary endpoints are:

1. Incidence of symptomatic ARIs of any severity
2. Incidence of non-infectious adverse events of interest††, overall and by severity grade (CTCAE classification)
3. Incidence of all-cause hospitalization or death (separately and combined)
4. Total antibiotic consumption, overall and by class
5. Viral load in air samples collected in communal living spaces
6. Viral, bacterial and fungal load on surface (fomite) samples collected in communal living areas
7. Incremental Cost-Effectiveness Ratio (ICER) of UVGI implementation.

(††) Keratitis and erythematous skin eruptions occurring in light-exposed areas.

### 5. STUDY POPULATION

---

#### 5.1. Inclusion criteria

##### Inclusion of centers:

Nursing homes:

---

\* Fomite = Inert object that can carry infectious agents, passive vector for disease transmission

- Having a system for monitoring cases of upper and lower respiratory infections in their residents
- Agreeing to take part in the study
- Undertaking to comply with the entire protocol
- Accepting the installation of UVGI devices
- Undertaking to provide all residents or their legal guardians/curators with an individual information leaflet

#### Inclusion of individuals

All residents who have at least one day's presence in one of the participating centers during one of the two calendar periods of the study (period 1: between October 1, 2024 and April 30, 2025; period 2: between October 1, 2025 and April 30, 2026) will be eligible.

#### **5.2. Exclusion criteria**

##### Exclusion of centers:

Nursing Homes will not be included in the study if:

- They are already equipped with another air treatment system (i.e. HEPA\*, ionization) in common living spaces
- They do not wish to be equipped in all the spaces needing to be equipped according to the trial coordinating investigator
- They have planned a major change to the structure (extension, renovation, closure, requalification, etc.) that could affect the study population and/or UVGI air treatment systems during the course of the study.

##### Exclusion of individuals:

Residents of participating centers who have expressed (personally or through a relative or legal representative) a wish that their personal data not be used for the study at any time between the start of the study and the analysis of the results will not be included in the study.

#### **5.3. Recruitment**

All residents of the participating Nursing Homes will be informed of the study by the study coordination team and the Nursing Home care team.

#### **5.4. Information and opt-out**

This study falls within the scope of Article L1122-1-4 of [French law no. 2012-300 of March 5, 2012](#) ("loi Jardé"), which stipulates that "*in the case of research whose methodological requirements are not compatible with the collection of consent under the conditions provided for in the second paragraph of Article L. 1122-1-1, the protocol submitted for the opinion of the relevant personal data protection committee may stipulate that consent is not sought [...]. No research mentioned in the first paragraph may be carried out on a person if he or she has opposed it*".

---

\* High Efficiency Particulate Air= very high density particulate air filter

Residents will be fully and fairly informed, in comprehensible terms, of the principles, objectives, constraints and expected benefits of the study. This information will be provided in the form of an individual written information notice, which will be given or sent to residents, their relatives and/or their legal representatives. This information notice will explain residents' right to object at any time to the collection of their personal data. Nursing staff and study coordinators will be available to answer residents' questions at any time.

Only documents approved by the ethics committee will be used for this study, in their latest version, to the exclusion of any other document.

No data will be collected if the resident or his/her representative expresses his/her opposition. If this objection is notified after the collection of personal data has begun, previously collected data will be deleted.

### **5.5. Exclusion period and participation in other research**

For the duration of their participation in the RESPROTECT study, residents may only participate in other interventional or observational studies that do not influence the occurrence, treatment or management of respiratory infections. The RESPROTECT sponsor must be consulted prior to inclusion in any other study.

Once their participation in the RESPROTECT study has come to an end (due to scheduled study termination or premature discharge), residents will be able to participate in other studies without delay.

### **5.6. Volunteer compensation**

No compensation is planned for this study.

## **6. PROTOCOL PROCEDURES**

---

### **6.1. UVGI air treatment systems**

The UVGI devices will be installed prior to the start of the study by a team of independent contractors, in accordance with the installation protocols described in paragraph 18.1.

This team will then carry out a commissioning visit before the start of the 1st period, followed by a maintenance visit during the wash-out period before the start of the 2nd period.

The deactivation filters will be:

- Installed in arm B during the commissioning visit, and removed during the maintenance visit.
- Installed in arm A during the maintenance visit.

Residents, Nursing Home staff, investigators, and members of the clinical trial unit in charge of data collection or processing will not be informed of the presence of the filters.

In all centers, UVGI devices will be switched on the day of the start of the 1st period, switched off on the day after the end of the 1st period, switched on again on the day of the start of the 2nd period and switched off again on the day after the end of the 2nd period. They will remain lit continuously during both periods. They may be turned off temporarily in the event of work being carried out on the ceiling.

## 6.2. Clinical and microbiological monitoring

### 6.2.1. Time T0

Time T0 corresponds to the period between informing residents and turning on the UVGI air treatment units.

The study coordinating team will explain to caregivers how to set up and use the UVGI equipment, and how to collect clinical, paraclinical and microbiological data throughout the study.

### 6.2.2. Time T1

Time T1 corresponds to the 1st experimental phase (October 1st 2024 to April 30 2025).

#### Baseline data

Baseline data for all participants will be collected from Nursing Home records and entered into the eCRF.

#### Morbidity episodes and mortality

Nursing staff will be responsible for monitoring the occurrence of respiratory infections and adverse events of interest, as well as reporting hospitalizations and deaths.

The occurrence of ARIs, AEIs, all-cause hospitalizations, and all-cause deaths will be reported weekly to the trial's clinical research assistants (CRAs) by a designated contact person at each center. The clinical features, as well as any additional examinations prescribed and their results, will be noted in the resident's medical record. CRAs will verify individual reports against predefined diagnostic criteria in the resident's record (and, in case of hospitalisation, in the hospital record) and classify each event as validated (criteria met), rejected (criteria not met), or deferred (uncertain classification pending review). The Clinical Event Review Committee (see section 9.4) will adjudicate deferred events and systematically review all hospitalization and death records. Validated events will be entered into the eCRF by the Clinical Research Assistants (CRAs).

CRAs and the CERC will have secure online access to the electronic care records of participating nursing homes and to hospital records for hospitalized residents. To ensure completeness of event collection, the nursing home software will be queried every three months to generate comprehensive lists of all discharges (death, hospitalization, return home, or transfer to another facility), as well as oxygen and anti-infective prescriptions. These data will be cross-checked against the study database, and any missing or inconsistent events will be investigated and adjudicated by the CERC, in accordance with best practices for independent endpoint review committees.

#### Microbiological monitoring of air and surfaces

Environmental monitoring will be performed to quantify pathogen contamination in the air and on surfaces within nursing home communal areas. Air and surface samples will be collected at baseline and every seven weeks during both study periods.

Air samples will be obtained using volumetric air samplers operating at standardized flow rates. Surface samples will be collected using tryptic soy agar (TSA) contact plates and sterile polyester-headed swabs (eSWAB) applied to predefined fomites. Two self-adhesive plastic fomites will be installed in each center — one in a dining room and one in a communal activity room.

Air samples will be analyzed by quantitative PCR (qPCR) assays targeting SARS-CoV-2, influenza A and B viruses, and respiratory syncytial virus, using the *Triplex Thermo Fisher TaqPath COVID-19, FluA/B, RSV Combo Kit* (Ref. A49867). Surface samples will be processed for bacterial and fungal detection by culture on TSA plates, followed by species identification using matrix-assisted laser desorption/ionization time-of-flight mass spectrometry (MALDI-TOF MS, Bruker Daltonics). Viral detection from fomites will be performed by qPCR (see details in section 18.2).

#### 6.2.3. Time T2

Time T2 corresponds to the wash-out period (April 1 to September 30, 2025).

During this phase, all UVGI devices will be turned off. No microbiological sampling of air or surfaces will be carried out. ARI and AES will not be monitored. Deaths, hospitalisations and opt-out request will continue to be monitored. New participants will be informed on the study, and their baseline data will be recorded.

#### 6.2.1. Time T3

Time T3 corresponds to the 2nd experimental phase (October 1-2025 to April 30, 2026). During this period, clinical, paraclinical and microbiological data will be collected in the same way as during T1.

#### 6.2.2. Time T4

Deaths and hospitalizations will continue to be monitored until May 31, 2026, in order to characterize any possible death or hospitalization occurring after the end of the 2nd period but possibly linked to an ARI or an AE that began before the end of the 2nd period.

### 6.3. Monitoring summary table

**Table 1. Follow-up of centers and individuals participating in the research**

	T0 (Sept 2024)	T1 (Oct 2024- Apr 2025)	T2 (May 2025- Sept 2025)	T3 (Oct 2025- Apr 2026)
Individual information of 'prevalent' residents	x			
Individual information of 'incident' residents		x	x	x
Collection of opt-out requests	x	x	x	x
UVGI system implemented	x			
UVGI systems filtered/unfiltered, according to randomization	0/x		x/0	
UVGI systems turned on		x		x
UVGI systems turned off	x		x	
Collection of baseline data from 'prevalent' residents	x			
Collection of baseline data from 'incident' residents		x	x	x
Monitoring of ARI a and AEI b		x		x
Monitoring of discharge, hospitalization and death		x	x	x
Pathogen sampling on test and air surfaces		x		x

aARI: upper respiratory infection (sinusitis, otitis media, nasopharyngitis, angina, tracheitis) and lower respiratory infection (bronchitis, pneumonia and COPD exacerbations). Symptomatic infection with SARS-CoV-2, influenza

or Respiratory Syncytial Virus will be considered by default as a respiratory infection, even in the case of dominant extra-respiratory symptoms.

bAEI: adverse event of interest (keratitis and erythema in exposed areas)

## 6.4. Premature study termination

### 6.4.1. Opposition to data collection

Residents will have the right to object to the use of their data at any time, without having to give reasons, and without this having any adverse effect on their surveillance and care. In the event of opposition to the collection of their data, care vigilance will continue and potential adverse events of interest will continue to be reported

### 6.4.2. Study premature termination

In the event of premature termination or suspension of the study by the sponsor, the latter will immediately inform the investigators, the centers, the competent authorities and the Ethics Committee of the termination or suspension of the study and the reasons for it.

## 6.5. Data collected

Study data will be transcribed by the healthcare staff involved in a clear and legible way in the source documents (medical records) and collected in the electronic case report form (eCRF) by the clinical research assistants who will electronically sign the case reports.

The information gathered for this study will be as follows:

### 6.5.1. Participants data

#### Baseline

- Investigating center code (automatic)
- Participant ID number (automatic)
- Participant date of birth (month/year)
- Gender
- Date of information on the study
- Date of inclusion in the study
- Dependency index : AG-GIR (Autonomie Gérontologie Groupes Iso Ressources) score
- Vaccination status (Covid19, Influenza, Pneumococcal)
- Comorbidities

#### Follow-up

- Date(s) and reasons for hospitalization
- Date and cause of death
- Date(s) and reason(s) for leaving (and re-entering, if applicable) the center
- IRA or AEI episodes
  - Symptoms
  - Additional tests
  - Diagnosis

- Antibacterial and antiviral treatments
- Hospitalizations
- Oxygen treatment
- Event outcome
- Vaccinations

#### 6.5.2. Center data

- Pathogens isolated in air and surface sampling
- Antibiotic consumption
- Characteristics of the ENH: number of residents, number of staffs.
- Significant modification of hygiene and care protocols, where applicable.
- Unforeseen change to the structure (e.g. fire, water damage, etc.) that could lead to a major modification of the structure (extension, renovation, closure, requalification, etc.) that could affect the study population and/or UVGI air treatment devices, during the course of the study.

## 7. STATISTICAL CONSIDERATIONS

---

### 7.1. Number of centers and individuals to include

Each Nursing Home will have an approximate size of 90 participants, with a small coefficient of variation. It is estimated that 80% of participants will be present in both periods. As recruitment is open to new participants, those who die or permanently leave their Nursing Home will be replaced, and the number of participants present in each Nursing Home will remain constant throughout the study.

The intra-cluster coefficient of variation (WP-ICC  $\rho$ ) is estimated at 0.1 (10% of ARIs are explained by the Nursing Home environment). The inter-period correlation (between-period ICC  $\eta$ ) is estimated to be negligible (the two periods are winter and one year apart). Cluster auto-correlation (CAC) is set at 0.5 (i.e.  $\eta=0.05$ ), a figure recommended when few hypotheses are involved (Giraudeau *et al*, Sample size calculation for cluster randomized cross-over trials. Stat Med 2008;27:5578-85). Individual auto-correlation (IAC) is set at 0.2. Assuming an ARI incidence of 17 per 100 patient-years in the absence of UVCI devices, it is estimated that 12 clusters need to be included to demonstrate a 50% reduction in ARI incidence, with a two-sided alpha risk of 0.05 and power of 80% (Kasza *et al*, Sample Size Calculation for Stepped Wedge and Other Longitudinal Cluster Randomised Trials. Stat Med 2020;39:1871-83; Hooper *et al*, Sample size and power calculations for open cohort longitudinal cluster randomized trials. Stat Med 2016;35:4718-28)

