### Objectives

**Primary objective:** to compare the incidence of severe acute respiratory infections (ARIs) between periods when nursing homes (NHs) are equipped with active UVGI systems and periods when the UVGI systems are inactive.

**Secondary objectives:** to compare, between periods with active and inactive UVGI:

1. Incidence of ARIs of any severity;
2. Incidence of all-cause hospitalization or death;
3. Incidence of adverse events of interest (AEIs)(erythema in skin areas exposed to light and keratitis), overall and by severity grade;
4. Antibiotic consumption;
5. Presence of respiratory pathogens in air samples and on fomites;
6. Potential medico-economic benefits associated with the installation of UVGI systems

**Type of study:** Multicenter, open cohort, cluster randomized crossover (CRCO) quadruple-blind placebo-controlled trial.

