## Endpoints

### *Primary endpoint:*

Incidence of severe\* symptomatic acute upper and lower respiratory infections\*\*

\* severe = leading to oxygen therapy, hospitalization or death

\*\* sinusitis, otitis media, nasopharyngitis, angina, tracheitis, bronchitis, pneumonia, pulmonary abscesses and COPD exacerbations. Documented symptomatic infections with SARS-CoV-2, influenza virus, or respiratory syncytial virus, will be considered by default as respiratory infections, even if extra-respiratory symptoms predominate.

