## 4. STUDY OBJECTIVES AND EVALUATION CRITERIA

### 4.1. Primary objective

The primary objective is to compare the incidence of severe acute upper and lower respiratory infections, between periods when Nursing Homes are equipped with active UVGI systems and periods when Nursing Homes are equipped with inactive UVGI systems.

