### Main analysis

The main comparison will focus on the incidence of first severe ARI between follow-up periods with an unfiltered UV device and follow-up periods with a filtered UV device. The numerator will be the number of people who experienced at least one severe ARI during a period. The denominator will be the cumulative time spent in the nursing home until the first ARI or exit from the period.

The result will be expressed as an incidence ratio with a 95% confidence interval.

In the first instance, the analysis will be carried out at the individual level. A generalized linear mixed model will be used, with a Poisson distribution or a negative binomial distribution in the case of overdispersion, a logarithmic link function and an *offset* term for the number of patient-years. The model will take into account not only intervention and period fixed effects, but also random effects at cluster, cluster-period, cluster-individual and individual levels. The correlation structure will be of the exchangeable block type.

In the second instance, if the model does not converge, we will perform the analysis at the cluster level (Hayes RJ, Moulton LH. *Cluster Randomised Trials*. CRC Press; 2017. <https://books.google.fr/books?id=iklrDwAAQBAJ> p197).

Sensitivity analyses will be carried out:

- Using the cumulative incidence of severe ARI as the endpoint, with the total number of severe ARI in the numerator and the cumulative time spent in the nursing home until exit from the period in the denominator. The model will be the same as the main model, with the addition of a random individual-period effect.
- By adjusting the model on the following variables: gender, age, GIR index. The last two variables will be measured at the start of each period.

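### The 12 homes and 80% power in Section 7.1 rest on an unlabelled, unsourced ARI rate of 17 per 100 patient-years, and even if that rate is severe ARI the stated inputs do not give 80% power for the primary comparison

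*Protocol*

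**What the plan says.** Section 7.1 begins "Assuming an ARI incidence of 17 per 100 patient-years in the absence of UVCI devices" and continues "it is estimated that 12 clusters need to be included to demonstrate a 50% reduction in ARI incidence", at two-sided alpha 0.05 and 80% power. Its other inputs are about 90 residents per home, a within-period ICC of 0.1 (itself described for ARIs without a severity limit), a cluster autocorrelation of 0.5, an individual autocorrelation of 0.2, and 80% of residents present in both periods. The works cited there are papers on sample-size methods. No source is given for the 17.

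The primary objective is limited to severe infection, in the Summary ("to compare the incidence of severe acute respiratory infections (ARIs) between periods when nursing homes (NHs) are equipped with active UVGI systems") and in Section 4.1 ("The primary objective is to compare the incidence of severe acute upper and lower respiratory infections"). The Summary defines the term: "severe = leading to oxygen therapy, hospitalization or death". Section 7.2, Main analysis, narrows it to first events: "The main comparison will focus on the incidence of first severe ARI between follow-up periods with an unfiltered UV device". Section 4.4 lists "Incidence of symptomatic ARIs of any severity" as a separate, secondary endpoint. Section 4.3 defines the primary endpoint as severe and then adds "all grades of severity combined".

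**The concern.** The power claim names a different quantity from the one the trial will test. Neither the assumed rate nor the assumed reduction is described as severe or as first events. The protocol separates severe ARI from ARI of any severity everywhere that it lists endpoints, so a reader cannot tell which of them the 12 homes were sized for.

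Two things are at stake. If the primary result is not significant, there is no planned power or detectable reduction for first severe ARI against which to judge it. And Section 7.2, Other points to watch, asks the DSMB to assess the endpoint against the observed incidence, which needs an expected incidence with a known definition.

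**Working it through.** **1. Which endpoint does the 17 describe?**

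For severe:
- Over 7 months, 17 × 7/12 = 9.9 per 100 residents. Section 2.1 gives a winter attack rate of 18–25% for ARI, about twice that. Spread over 7 months (an assumption), 18–25% is 18 ÷ (7/12) = 30.9 to 25 ÷ (7/12) = 42.9 per 100 patient-years.
- Section 2.1 gives 1 lower respiratory infection per 1,000 resident-days, that is 0.001 × 365.25 × 100 = 36.5 per 100 patient-years, already above 17.
- The protocol drops the word severe elsewhere when describing the primary analysis: in the numerator in the Summary, and in the denominator in Section 7.2.

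Against settling it:
- Section 4.3 still carries "all grades of severity combined".
- Section 7.2, Other points to watch, says that the investigators hesitated between all ARIs of any severity and severe lower ARIs only, for want of reliable recent data. The present endpoint (severe, upper and lower) is neither.
- Applying Section 2.1's 10–50% hospital transfer (a pneumonia figure, so an assumption) to 36.5 gives 3.7–18 per 100 patient-years. On that reading 17 lies near the top of a severe range.

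**2. Does the stated 80% follow if 17 is the severe rate?**

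Two-period crossover, block-exchangeable correlation, K = 12 homes, m = 90 residents per home-period, normal approximation:

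DE = 1 + (m−1)ρ − mρ·CAC − (1−ρ)·IAC·retention = 1 + 8.9 − 4.5 − 0.9 × 0.2 × 0.8 = 5.256

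Var = 2·s²·DE/(K·m), where s² is the mean of p₀(1−p₀) and p₁(1−p₁) and p₁ = p₀/2

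Power = Φ[(p₀−p₁)/√Var − 1.96]

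| Reading of 17 | p₀ | p₁ | s² | SE | z | Power | Homes for 80% |
|---|---|---|---|---|---|---|---|
| Rate over 7 months | 0.0992 | 0.0496 | 0.0682 | 0.0258 | 1.924 | 49% | about 25 |
| Risk per period | 0.170 | 0.085 | 0.1094 | 0.0326 | 2.604 | 74% | about 14 |
| Rate over 14 months | 0.198 | 0.099 | 0.1242 | 0.0348 | 2.853 | 81% | 11.6 |

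With the stated correlations, 80% with 12 homes appeared only when the rate was applied to 14 months, although a resident has only 7 months per condition. Whether that is how the 12 was obtained cannot be known from the protocol.

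Other variance forms and scales (pooled, control-only, Poisson, log, logit, arcsine) give 39–49% for the first row and 63–75% for the second. A t reference with 10 degrees of freedom gives about 41% and 65%. Section 7.1 also calls the between-period correlation negligible; setting it to zero lowers the first row to about 29%.

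**3. Smallest reduction detectable with 80% power**

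Same formula, in whole percentage points:
- Rate over 7 months, 69%: p₁ = 0.0307, s² = 0.0596, SE = 0.0241, z = 0.0684/0.0241 = 2.84, power 81%. At 68% it is just under 80%.
- Risk per period, 54%: p₁ = 0.0782, s² = 0.1066, SE = 0.0322, z = 0.0918/0.0322 = 2.85, power 81%. At 53% it is just under 80%.

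**4. If 17 is instead an any-severity rate (illustration only)**

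The protocol gives no severe fraction. Assume one half. Control events fall from 1,080 × 0.0992 = 107 to 54. Power for severe ARI then depends on what is held constant:
- The between-home coefficient of variation (ICC = CV²·p₀/(1−p₀), falling to about 0.047 for the rate reading and 0.045 for the risk reading): 43% (rate) or 67% (risk).
- The ICC of 0.1: 26% (rate) or 42% (risk).

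**The case against.** The best defence is that ARI in Section 7.1 is shorthand for severe ARI. The protocol shortens the term in the same way when defining its primary analysis, and an any-severity rate of 17 fits Section 2.1 poorly. That is fair, and it limits the point. A reader might infer that the trial was sized for its secondary endpoint; the text does not show this, and the background rates lean the other way. The power figures that depend on an assumed severe fraction therefore carry little weight.

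Second, the protocol openly admits that its incidence data were poor and has the DSMB compare the endpoint with observed incidence while preserving the blind. That is a real safeguard, but it supplies neither the label nor a power figure.

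Third, Version 3 is dated after period 1, the 12 homes are fixed, and the result will be read from its 95% confidence interval. All true, so this is a correction to a stated figure rather than a reason to change the trial.

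It is also tempting to conclude that adding the word severe and a reference would close the matter. It would not: on the stated inputs, 12 homes give about 49% or 74% power for first severe ARI, so a relabelled Section 7.1 would still state a power that this calculation does not return.

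**Conclusion.** The point holds as a fault in a stated figure. Section 7.1 does not tie its 80% power to first severe ARI, and the 17 has neither a definition nor a source. On the reading most favourable to the protocol, that 17 is already the severe rate, power with 12 homes is about 49% over 7 months or about 74% if 17% is a per-period risk. The smallest reductions detectable with 80% power are about 69% and 54%, against the 50% assumed. These figures rest on the protocol's own correlations, equal home sizes and a normal approximation with a simplified retention term; that term moves power by less than 2 points, and a t reference lowers the figures.

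Whether the true rate differs from 17 is not shown. If 17 covers all severities, power for severe ARI is lower still, by an amount the protocol does not fix. Confidence is high on the missing link and on the failure to reproduce 80%. There is no claim that 17 is wrong. The correction should be made, but it does not threaten the validity of the analysis.

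**What to change.** In Section 7.1, state which endpoint the 17 describes, give its source, and say whether it is a rate per patient-year or a risk per period. Whichever answer is given, state the expected control incidence of first severe ARI over 7 months and restate the power, or the smallest detectable reduction, of the 12 homes for that endpoint. Do this without unblinded data. In Section 4.3, delete "all grades of severity combined".

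The cost is a label, a source, one recalculation and one deleted phrase. No homes are added, nothing is unblinded and the analysis does not change. The downside is that the stated power becomes less favourable.

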### Intervention

In all the Nursing Homes included, UVGI devices will be installed and commissioned at the start of the study. These UVGI devices can be deactivated by installing an invisible internal filter. The inactivation filters will be installed by a technical team independent of the investigation team. Inactivation will therefore be carried out blind to the care givers and the investigation team.

The centers included will be randomized into two arms:

- In arm A: the UVGI device will be left active during period 1, and filtered/deactivated during period 2.
- In arm B: the UVGI device will be filtered/deactivated during period 1 and left active during period 2.

The two periods will last 7 months each, and will take place two years in a row on the same dates (October 1 to April 30). They will be separated by a 5-month wash-out period (May 1 to September 30), during which all UVGI devices will be switched off in both arms.

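### Section 7.1's 80% power with 12 homes does not follow from its inputs on their most direct reading, and cannot be verified because the ICC scale is unstated and two values of the between-period ICC are given

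*Protocol*

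**What the plan says.** Protocol section 7.1 gives the sample size justification. It assumes about 90 residents per home with leavers replaced, and 80% of residents present in both periods. The within-period ICC "is estimated at 0.1 (10% of ARIs are explained by the Nursing Home environment"), although the same sentence names the quantity a coefficient of variation. The between-period ICC "is estimated to be negligible (the two periods are winter and one year apart"). The next sentence reads "Cluster auto-correlation (CAC) is set at 0.5" and spells out the resulting between-period ICC as 0.05. IAC is 0.2. The event rate and target follow: "Assuming an ARI incidence of 17 per 100 patient-years" without active devices, and "it is estimated that 12 clusters need to be included to demonstrate a 50% reduction in ARI incidence". The claimed power for this is 80% at a two-sided 5% level.

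Two other places matter. The Summary (Intervention) and section 3.3 fix the exposure: "The two periods will last 7 months each". The main analysis in section 7.2 is a log-link Poisson or negative binomial mixed model with an offset "term for the number of patient-years" and random effects for home and home-period. Section 7.1 cites methods papers but shows no formula, no scale for the ICC, no expected number of events per period and no reference distribution.

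**The concern.** The 80% is stated as a result of listed inputs, so a reader should be able to recover it. Three features prevent that.

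- The rate is annual and the periods are 7 months, so a resident expects 0.17 × 7/12 = 0.0992 events per control period, not 0.17. Section 7.1 shows no per-period figure.
- An ICC of 0.1 means very different between-home variation on the outcome scale and on the latent scale of a log-link or logit model. The scale is not given. The gloss that 10% of ARIs are explained by the home suggests the outcome scale.
- The between-period ICC is what a crossover subtracts from its variance. Calling it negligible and setting it at half the within-period ICC are two different designs for power purposes.

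A null result will be read against the claimed 80%. If the direct reading is what was meant, the trial had roughly an even chance of detecting a halving of incidence. The confidence interval will show the precision achieved, so the damage is confined to the planning statement.

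**Working it through.** **Inputs** (section 7.1 unless noted): K = 12 homes, m = 90, ρ = 0.1, CAC = 0.5 so η = 0.05, IAC = 0.2, overlap 0.8, control rate 0.17 per patient-year, halved under UVGI, two-sided 5%. Period length is 7 months (Summary; section 3.3). Power is Φ(z − 1.96) unless t on 10 df is stated.

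**1. Outcome-scale ICC, open-cohort block-exchangeable formula**

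Variance multiplier = [1 + (m − 1)ρ] − [mη + (1 − ρ) × IAC × overlap] = 9.9 − (4.5 + 0.9 × 0.2 × 0.8) = 9.9 − 4.644 = 5.256.

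Variance of the difference = 5.256 × s / (90 × 12), where s is the sum over conditions of p(1 − p) (binomial) or of the expected counts per resident (Poisson).

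*Attempt to reproduce the plan, with 17% vs 8.5% as a full-period risk:* s = 0.1411 + 0.0778 = 0.2189; SE = √(5.256 × 0.2189/1080) = 0.0326; z = 0.085/0.0326 = 2.60; power 74%. Homes for 80%: (1.96 + 0.842)² × (5.256 × 0.2189/90)/0.085² = 13.9, so 14.

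*With 7-month periods, 0.0992 vs 0.0496:*
- Binomial: s = 0.1365; SE = 0.0258; z = 1.92; power 49%; 25.4, so 26 homes for 80%.
- Poisson: s = 0.14875; SE = 0.0269; z = 1.84; power 45%; 27.7, so 28 homes.

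*Reduction detectable with 80% power, 12 homes, 7 months, binomial:* about 68%. Check: 0.0992 vs 0.0315 gives s = 0.1198, SE = 0.0241 and z = 0.0677/0.0241 = 2.80.

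**2. Latent-scale ICC, 7-month periods**

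Per-home variance of the log rate ratio = 1/(90 × 0.0992) + 1/(90 × 0.0496) + 2(1 − CAC)S = 0.336 + S at CAC 0.5, or 0.336 + 2S at η = 0. Here S = (0.1/0.9) × level-1 variance. The logit row uses p(1 − p) in the sampling terms (0.360) and a log odds ratio of 0.747.

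| Level-1 variance | S | Power, normal | Power, t (10 df) | η = 0, normal |
|---|---|---|---|---|
| π²/6 (complementary log-log) | 0.183 | 92% | 85% | 82% |
| ln(1 + 1/λ), control rate | 0.267 | 87% | 80% | 73% |
| ln(1 + 1/λ), mean rate | 0.297 | 86% | 78% | 70% |
| π²/3, logit | 0.366 | 86% | 78% | 70% |
| π²/3 placed on the log rate | 0.366 | 82% | 73% | 64% |

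These rows leave out the IAC term. Including it raises the mean-rate log row and the logit row to about 88%.

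**3. Effect of a negligible between-period ICC on the outcome scale**

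With η = 0 the multiplier is 9.9 − 0.144 = 9.756. For 7-month periods (binomial), SE = √(9.756 × 0.1365/1080) = 0.0351; z = 1.41; power 29%. With 17% vs 8.5% as a full-period risk, z = 1.91 and power 48%.

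**The case against.** The strongest reply is that the planned model has a log link and home-level random effects, so a latent-scale ICC is a natural choice, and a share-of-variance gloss can describe a latent ICC too. On that scale 12 homes give 82–92% with a normal reference and 73–85% with t on 10 df, and some conventions land almost exactly on 80%. The cited methods papers may have led the authors there. This stands, and it rules out four stronger readings that a reader might infer.

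- *That the inputs cannot give 80% at all.* The documents do not support this, because 80% lies within the latent range.
- *That the annual rate was never converted to 7 months.* Section 7.1 shows no calculation, so the absence of a displayed conversion proves nothing either way.
- *That a between-period ICC near 0 sinks 12 homes on any scale.* One latent convention still gives 82% (73% with t on 10 df).
- *That a single corrected figure can be supplied on the latent scale.* The answer depends on the level-1 variance, so one point value would be falsely precise.

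It can also be said that the operative between-period value is explicit, since CAC 0.5 and 0.05 are written out. That is fair, but the adjacent sentence still asserts something incompatible.

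The outcome-scale result has its own convention: home effects are additive. Converting the same ICC to a log-normal home effect gives about 57–68% with 7-month periods, still short of 80%. Other routes to about 80% contradict the text. Fourteen months of exposure per period (81%, outcome scale) conflicts with the 7-month periods. A logit ICC with 17% as a per-period risk and η = 0 (80%) drops both the period length and CAC 0.5. Taking 0.1 literally as a coefficient of variation gives about 98%, but the section treats it as an ICC when it derives 0.05 = 0.5 × 0.1.

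**Conclusion.** The point holds as a failure of the most direct reading and of verifiability, not as proof that 12 homes is wrong. With an outcome-scale ICC of 0.1 and the section's other inputs, power is about 74% if the annual rate is used as a full-period risk, and about 45–49% with 7-month periods (additive home effects, normal reference). The 80% is recovered within the document's period length and CAC only by assuming a latent-scale ICC that the section does not state.

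The contradiction over the between-period ICC needs no modelling choice to see. It matters because a value near 0 takes 7-month power to about 29% (outcome scale) or 64–82% (latent, normal reference).

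This should be fixed. Confidence is medium, because the scale and formula that the authors used are not visible.

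**What to change.** Keep 12 homes and rewrite the paragraph in section 7.1:

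- Show the expected events per 7-month period (0.0992 vs 0.0496 per resident; about 8.9 vs 4.5 per home of 90).
- State the scale on which the ICC of 0.1 applies, the formula with its level-1 variance, and whether a normal or t reference is used. Call the quantity an ICC throughout.
- Delete the statement that the between-period ICC is negligible, or otherwise give one value.
- Restate the power of 12 homes, or the reduction detectable with 80% power, on that basis. If the ICC is on the outcome scale, the stated 80% must be replaced by about 45–49%. If it is latent, report the figure that the stated convention and reference distribution give.

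The cost is one paragraph and possibly a less favourable stated power. Protocol version 3 is dated 23/09/2025, after period 1 ended, so the number of homes is in practice settled. Residents, endpoint and analysis are unchanged.
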